8.4 Procedures

Baseline biometric measures (HbA1c, fasting glucose, weight, BMI, blood pressure and lipid panel) will be collected utilizing the most recent values available in the subjects' medical records within the year prior to enrolling in the FFF study. These biometric measures will be used to determine eligibility for the study and during data analysis.

A set of blood tests (HbA1c, fasting glucose and lipid panel) will be collected for research immediately prior to the subject beginning the FFF program (month 0 for treatment group or approximately month 6 for the control group). In addition, research participants will complete a baseline survey upon entry into the FFF program. This survey will be completed on site at the FFF program clinic.

A set of research biometric measurements (HbA1c, fasting glucose, weight, BMI, blood pressure and lipid panel) will be collected at approximately the 6 and 12 month time points (plus or minus

1 month) for the treatment group. A set of research biometric measurements (HbA1c, fasting glucose, weight, BMI, blood pressure and lipid panel will be collected at approximately the 12 month time point (plus or minus 1 month) for the control group.

In addition, all research participants will complete a survey after 6- and 12-months of participation (similar to the baseline survey) during FFF program visits. For those who do not enroll in the study, we will not continue to investigate their outcomes at these intervals.

Protocol required lab draws will be paid for by the study. Patients will be compensated with a \$50 gift card for the time and effort to complete the lab work and the patient surveys.

Based on our experience with the FFF program, we expect nearly all the patients to continue with the study. For the few who do drop out of the study but remain in the program, we will contact these subjects and collect outcome information, including clinical lab results and the ongoing survey. For those who drop out of the FFF program, but remain in the study the lab work will be covered by the research study and the surveys will be completed by phone or e-mail. The patients will be offered a \$50 gift card as compensation.

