8.4.1 Study Time and Events Table

[figure not shown]
Study timeline (calendar time, H1=January-June, H2=July-December):

	2018	2018	2019	2019	2020	2020	2021	2021	2022
	H1	H2	H1	H2	H1	H2	H1	H2	H1
Planning									
Enrollment									
Outcome tracking									
Analyze impact									
Manuscript preparation									

[figure not shown]
Study timeline (subject point of view):

[figure not shown]
Treatment							
Study Activity	Enrollment	Month 6	Month 12	Month 24			
Informed Consent ¹	Х						
Randomization	Х						
FFF Program Initiation ⁵	Х						
Survey ³	Х	Х	Х				
Research Labs ⁴	Х	Х	Х				
Health Care Utilization Review (EMR)	X						

Control							
Study Activity	Enrollment	Month 6	Month 12	Month 24			
 ¹ Patients will be asked to provide verbal consent over the phone. ² FFF program start will occur approximately 6 months after consent for Control patients. ³ Redcap surveys will be administered by FFF staff during program visits. ⁴ Research labs include: HbA1c, Fasting Glucose, lipid panel ⁵ FFF program start will occur within 1 month after consent for Treatment patients. 							
Research Labs ⁴ X X							
Health Care Utilization Review (EMR)	X						

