The coefficient β_1 measures intent-to-treat: the causal effect of being randomized into the treatment group. This can differ from the effect of the program if there is non-compliance: some subjects in the treatment group may decide not to join the program or join for a very short time. At the initial pilot site, 17% of those who begin the program are no longer in the program at 6 months. We plan to record outcomes for all subjects regardless of program participation and will estimate the equation using Two Stage Least Squares (2SLS), with the initial treatment assignment used as an instrumental variable for ultimate assignment. The 2SLS estimate measures the average causal effect of the program for those who choose to remain in it as a complementary parameter to the intent-to-treat analysis. In addition, if there is differential attrition from the study across treatment and control groups—despite our efforts to obtain outcomes from each subject including obtaining multiple forms of contact information for subjects and their family members and compensation for subjects' time, we will explore bounding estimates under a range of assumptions about effect sizes for those not observed.

For survey responses, we will consider answers in the top and bottom categories as separate outcomes and will test robustness to using nonlinear estimators. For patient satisfaction, we will calculate the net promoter score as an outcome as well. To avoid concerns about multiple hypothesis testing, each category of questions will be compiled into an index and we will report p-values corrected for the multiple tests when presenting results for each question individually.

In addition to outcome comparisons across all of the participants, we will consider heterogeneous treatment effects in three ways. First, a priori we are interested in whether the program is

CONFIDENTIAL AND PROPRIETARY

[figure not shown]

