Recruitment will be conducted over the phone; the program will be described, consent will be sought, and then patients will be randomized to either treatment ("start FFF now") or control ("start FFF later"). Note that all patients eligible for FFF, whether or not they agree to participate in the study, will be randomized to determine the timing with which they will enroll in FFF. This is the way the program is being introduced, akin to a lottery, and ensures that there is no incentive to refuse to participate in the study in order to start FFF sooner. Recruitment staff will discover whether the patient is randomized to start now or start later in a tamper proof REDCap application, which consults a randomized allocation table that the recruiter cannot access and a treatment status that is locked along with the patient's identifying information and study ID. The recruiter will then set up the patient's first appointment for those in the treatment group and will reach out to patients 5 months later to set up appointments for the group randomized to start later. We anticipate finding the patients 5 months later because all subjects are Geisinger Health patients, whose current address is on file, and we will ask for two other contacts at the time of recruitment.

The randomization is stratified using levels of HbA1c: <8.0 (in the event that the threshold is lowered),  $\geq$ 8.0 and <9.5, and  $\geq$  9.5 to attempt to ensure balance on a key pre-study control and because we are interested in estimating effects separately by these categories to inform

threshold setting in future applications. The randomization happens separately by location (Scranton and Lewistown) as well.

The trial will launch in April 2019 in Scranton, and likely June 2019 in Lewistown. We plan to continue enrollment until we attain at least 500 subjects (half in treatment) or when the recruitment period has lasted 2 years. If recruitment slows, we will consider lowering the eligibility threshold to an HbA1c of at least 7.5 rather than 8.0, and we may consider expanding the geographic limit.

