### 3. Data sources and outcomes

### 3.1. Data sources

There are three main sources of data:

A. Geisinger Health Electronic Health records. These include clinical outcomes that are collected as part of the study. Subjects go to a Geisinger lab for a blood test at no cost (more on potential attrition is discussed below); the blood is tested for HbA1c, fasting glucose, total cholesterol, LDL cholesterol, and triglycerides. Weight, BMI and blood pressure are also recorded. The records also include inpatient, outpatient, and ED encounters, and scheduling information. All subjects are Geisinger Health patients. Utilization is largely at Geisinger facilities, although inpatient stays at other hospitals may be visible in the EHR record.

- B. Fresh Food Farmacy operational data. This includes encounter data at FFF, including number of weeks in which the patient picked up food, their choices of food, dietitian appointments, and classes. Program participants are surveyed upon entry into FFF, and again at 6 months and at 12 months, and the surveys have been modified to measure outcomes of interest. This will allow us to ask questions about diet, healthy behaviors, self-efficacy, and self-assessed health.
- C. Geisinger Health Plan data. For subjects who receive their insurance from the Geisinger Health Plan, expected to be more than half of the subjects, paid claims are available. This

allows us to measure utilization at providers other than Geisinger Health, albeit on a smaller and selected sample. Highmark (another local insurer) may share utilization data for their patients that are participating in the program as well.

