### 12-month outcomes

We will examine the same outcomes at 12 months as we did at 6 months. In doing so, we will be comparing the treatment group (which will have had 12 months of exposure to the FFF program) to the control group (which will have had 6 months exposure to the FFF program). This will be informative about whether the rate of expected improvement in outcomes slows over time.

Health care utilization will also be examined at 12 months. As mentioned earlier, we expect that any effect of FFF on utilization may be visible only with a lag. We have statistical power for the more common 12-month outcomes: any inpatient stay, any ED visit, and any hospital visit (inpatient or ED). We will also examine the number of such visits, as well as the number of outpatient visits outside the Fresh Food Farmacy.

To allow time for the program to affect outcomes, we will also consider outcomes within other timeframes: 90-365 days and 90-180 days.

The program re-assesses food insecurity after one year, so food insecurity will be asked at 12 months; given the nature of the program we hypothesize that the FFF program should considerably reduce food insecurity.

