For survey responses that include categorical answers, outcomes will be binary measures of whether the answers are in the top and bottom quintiles as separate outcomes and will test robustness to using nonlinear estimators such as the multinomial logit. To avoid concerns about multiple hypothesis testing for multiple measures within each category of questions (diet, other healthy behaviors, diet understanding, diabetes understanding, self-assessed health, self-efficacy, and patient satisfaction), we will compile answers to these questions into indexes and test effects of the program on a change in these indexes. We will also report p-values corrected for the multiple tests when presenting results for each question individually.

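### Food insecurity has no planned follow-up while controls are unexposed, and the survey-index change and initial-knowledge split need defining because neither arm has a described pre-randomization survey

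*SAP*

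**What the plan says.** **Survey timing.** Protocol 8.4 states that "research participants will complete a baseline survey upon entry into the FFF program", on site at the programme clinic. SAP 3.1 agrees: "Program participants are surveyed upon entry into FFF, and again at 6 months and at 12 months". A footnote to Protocol 8.4.1 adds "Redcap surveys will be administered by FFF staff during program visits". Consent and randomization come earlier, by phone, and no survey step is described there (SAP, Enrollment & Randomization). Treatment subjects start within a month of consent and controls at about six months.

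**Survey indexes.** SAP 4: "we will compile answers to these questions into indexes and test effects of the program on a change in these indexes". Protocol 9.1.1 says only that "each category of questions will be compiled into an index", and Protocol 8.6 describes comparing answers between arms; neither mentions a change score. SAP 4 defines the lagged outcome for clinical tests and utilization only. It also lists a model with strata indicators plus the lag, and does not say whether that model applies to surveys.

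**Food insecurity.** It is an entry criterion, from a two-question screen (Protocol 8.2.2; SAP, Enrollment & Randomization). On follow-up, SAP 3.3 (12-month outcomes) says "The program re-assesses food insecurity after one year, so food insecurity will be asked at 12 months", and there the SAP expects a marked reduction. The SAP's 6-month outcome list does not include it.

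**Knowledge subgroup.** SAP, Planned Heterogeneity Analysis, splits the sample at the median of a score built from the baseline survey's diabetes and diet questions.

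**The concern.** Month 6 is the only planned survey time at which controls have not yet received the programme. Food insecurity is the condition the programme targets, yet the plan measures it only after both arms have been exposed. If the item reflects current status and the effect builds quickly, the arms will have converged by then, and a small difference could be misread as a failure to relieve food insecurity.

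For the indexes, the word change admits several estimands with different expected values. One cannot be computed for controls, and another compares treated subjects with treated subjects. The SAP exists to fix such choices before results are seen.

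The knowledge split treats a score taken after randomization, about six months apart between arms, as if it were a common baseline characteristic.

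**Working it through.** The documents give no effect size, prevalence or power for the survey indexes or food insecurity, so there is no stated figure to reproduce. The check is a timeline followed by arithmetic on labelled assumptions.

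**1. Timeline** (Protocol 8.4 and 8.4.1; SAP 2, 3.1 and 3.3)

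| Trial month | Treatment | Control |
|---|---|---|
| Before randomization | eligibility screen; no survey described | eligibility screen; no survey described |
| 0 (within about 1 month) | entry survey | none |
| 6 | 6-month survey, 6 months of FFF | entry survey, no FFF yet |
| 12 | 12-month survey, 12 months of FFF | survey, 6 months of FFF |

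The control arm's survey row in the events table is not legible in the text reviewed, so this rests on the prose and the footnote, which agree.

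**2. What an index change could mean.** Let d be the effect of the first six months of FFF and g×d the further effect of the next six.

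- Pre-programme to trial month 6: treatment has both values; controls have no starting value. Not computable. The strata-plus-lag model fails for the same reason.
- Own entry to six months in FFF: d − d = 0. Treated is compared with treated.
- Own entry to trial month 12: (d + g×d) − d = g×d.
- Level at trial month 6: d − 0 = d.

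Only the last estimates FFF against no FFF. With 250 per arm (500 randomized 1:1), two-sided 5% and 80% power, and everyone surveyed, the detectable level difference is (1.96 + 0.84) × √(2/250) = 0.25 SD.

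**3. Food insecurity.** Let d6 and d12 be the effects after 6 and 12 months of FFF, and f = d6/d12 (assumed). For a current-status item the month-6 contrast is d6 and the month-12 contrast is d12 − d6, so their ratio is (1 − f)/f:

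- f = 0.4: 0.6/0.4 = 1.5
- f = 0.5: 1.0
- f = 0.6: 0.4/0.6 = 0.67
- f = 0.75: 0.25/0.75 = 0.33

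The recall window matters as much. Take the report as the average effect over a window of w months, with effect profile 1 − exp(−kt) and k = ln(3)/6, which gives f = 0.75. Contrasts as shares of d12:

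| w (months) | Month 6 | Month 12 | Ratio |
|---|---|---|---|
| 0 | 0.75 | 0.25 | 0.33 |
| 1 | 0.71 | 0.27 | 0.38 |
| 3 | 0.63 | 0.33 | 0.53 |
| 6 | 0.44 | 0.46 | 1.0 |
| 12 | 0.22 | 0.45 | 2.0 |

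As an illustration of scale, take a current-status item, unexposed prevalence of 60% to 90% (assumed), 250 per arm and a two-proportion normal approximation. A month-6 contrast has 80% power for an effect of 8.8 to 12.5 points. For the month-12 contrast to reach 80% power, the 6-month effect must be 11.0 to 12.5 points at f = 0.5, 17.7 to 18.7 at f = 0.6, and 31.6 to 37.4 at f = 0.75.

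**4. Possible bias in a month-6 item.** If a share x of food-secure controls report insecurity while joining, the bias in favour of FFF is x(1 − p0), with p0 the true control prevalence. For x from 5% to 20% and p0 from 90% to 60%, it runs from 0.05 × 0.10 = 0.5 points to 0.20 × 0.40 = 8 points.

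**5. Knowledge split.** From the timeline, the score is taken at about month 0 in one arm and month 6 in the other, after randomization in both, and only in entrants.

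**The case against.** **The index wording is a clarification.** This largely stands. Protocol 8.6 and 9.1.1 describe arm comparisons of answers and an index without a change score. The SAP's primary specification is a level model, and its strata-only variant needs no lag. A reader might infer that the survey analysis is impossible; the documents do not support that, because the month-6 level comparison can be estimated. What remains is that the SAP does not say this is the test.

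**Controls are not alone in lacking a baseline.** Correct. A reader might infer that only controls lack one, but the treatment arm's first survey also follows randomization, though it precedes exposure. Nor is the month-6 level comparison automatically sound: it is limited to people who enter the programme, so it inherits any selection at entry. The SAP's bounding for differential attrition is the relevant provision.

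**The 12-month timing is disclosed and has a reason.** True: the programme re-assesses at one year, and the SAP states the 12-versus-6-month exposure. A month-6 item would therefore be an addition to the plan. The instrument is not in the documents, so the entry survey may already carry the questions; no month-6 analysis of them is planned.

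**Harm is not shown.** A reader might infer that the 12-month item is bound to be weak. The documents give neither the recall window nor the speed of the effect. With a slow effect, or a window of six months or more at f = 0.75, it loses nothing.

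**Timing is ambiguous.** Protocol 8.4 speaks of months of participation without saying whether in the study or in FFF. If the one-year re-assessment ran on programme time, controls would be asked near trial month 18.

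**The added item has its own bias.** This stands: at the extreme of the assumed range, 8 points, it is not small beside a detectable effect of 12.5 points at 60% prevalence.

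**Conclusion.** The point holds as a cheap improvement to secondary and exploratory survey outcomes. HbA1c at 6 months does not depend on the surveys.

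Three things follow from the documents without assumptions. Food insecurity has no planned follow-up while controls are unexposed. No pre-randomization survey is described for either arm, so a within-person index change to month 6 and the strata-plus-lag model cannot be computed for controls. The initial-knowledge score is not a common baseline moderator.

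How much the food-insecurity timing costs is not established. At f = 0.75 the month-12 contrast is between 0.33 and 2.0 times the month-6 contrast, depending on the recall window; for a current-status item it runs from 1.5 at f = 0.4 to 0.33 at f = 0.75. The effect profile, prevalence, recall window and over-reporting rates are all assumptions, so the power figures show scale only.

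**What to change.** **Food insecurity.** Ask the two questions at about trial month 6 in both arms: on the treatment 6-month survey, and on the control entry survey before FFF starts. State the same recall window for both. Report the month-6 arm difference as FFF versus no FFF. Keep the 12-month result, label it 12 versus 6 months of exposure, and state that it is asked at trial month 12. If the entry survey already carries the items, only the analysis needs adding.

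**Index test.** State in SAP 4 that the test is the arm difference in index level at trial month 6, adjusted for strata and demographics, with no survey lag, and that the strata-plus-lag model does not apply to survey outcomes.

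**Non-entrants.** Seek the survey by phone or e-mail from non-entrants in both arms. Protocol 8.4 already provides that "the surveys will be completed by phone or e-mail", but only for programme dropouts who stay in the study. For controls there is also an existing call, since recruiters "will reach out to patients 5 months later to set up appointments for the group randomized to start later". Either route is a new procedure. Apply the SAP's bounding to those still missing.

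**Knowledge split.** Label it exploratory and not a common baseline moderator, or drop it.

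**Cost.** Two questions on scheduled surveys, some phone or e-mail follow-up, and SAP wording. Downsides to state: controls may over-report need while joining; a short recall window would differ from the eligibility item if that uses a longer one; phone and on-site answers may differ; and the indexes gain no precision from a survey baseline.

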### Planned Heterogeneity Analysis

In addition to outcome comparisons across all of the participants, we will consider heterogeneous treatment effects across patients. First, a priori we are interested in whether the program is especially effective for different levels of baseline HbA1c in order to help target the program in the future. For example, if effect sizes decrease with the baseline A1c, we may want to expand the program to those with A1c  $\geq$  7.5.

We are also interested in whether the program has different effects across the two locations (Scranton and Lewistown) to investigate the external validity of the estimates.

We will also test for different effects of the program by sex, as the cooking instruction may differ in effectiveness for men versus women. Household structure may be important given that the food goes to the household: differences between single and multi-person households will be estimated.

We hypothesize that the FFF program may have greater impacts among those of lower income (for whom the food may be especially helpful) and may vary across education levels (those with more education may be better able to utilize the information they are given about food preparation and diabetes management or they may already possess that information); these hypotheses will be tested using ZIP code level education and income measures, although there

may be little variation. We will also test differences by type of payer, with Medicaid providing another proxy for income as well as independent interest in effects for this group given interest among Medicaid systems in this type of intervention.

To further investigate the importance of information, we can compare results for individuals who score relatively well on the baseline survey questions about understanding of diabetes and diet. We will create a score for those questions and split the sample based on the median value of the initial knowledge. Another source of heterogeneity that could be considered in other contexts is the cost of using the program. We plan to compare results by distance between home and the clinic based on the median distance to the clinic from the residential ZIP code.

HbA1c can be affected by diet, lifestyle, and drug adherence. To consider the latter, we will compare patients who are on insulin versus those who are not on insulin at the start of the trial.

We plan to consider whether machine-learning techniques to choose the optimal controls in X and to shed light on the types of patients where the effects are particularly large are feasible with the given sample size and statistical power. This will likely entail normalizing the outcomes so that we measure effects relative to each participant's baseline rather than absolute differences.

Interim results from the trial will be monitored on an ongoing basis by the MIT/J-PAL researchers (Drs. [name], [name] and [name]), while the clinician team will be blinded from these interim results so that such results do not affect program management in a way that would not be feasible outside of the study setting. Such blinding adds credibility to the results so that they are more likely to apply to other programs in the future that are not part of a study.

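### The knowledge subgroup is split on a survey taken about six months later in controls than in treated subjects, so the comparison within each half is not randomized

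*SAP*

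**What the plan says.** In SAP section 4, Planned Heterogeneity Analysis, the authors want to learn how much information matters. They write that "we can compare results for individuals who score relatively well on the baseline survey questions about understanding of diabetes and diet", and that they will score those questions and "split the sample based on the median value of the initial knowledge". They do not say whether the median is pooled or taken within arm. The paragraph on insulin in the same section does fix its subgroup in time: "we will compare patients who are on insulin versus those who are not on insulin at the start of the trial".

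Protocol 8.4 says when and where the survey happens: "research participants will complete a baseline survey upon entry into the FFF program", and "This survey will be completed on site at the FFF program clinic". SAP 3.1 (item B) agrees that the first survey is at FFF entry, and footnote 3 of the table in Protocol 8.4.1 has FFF staff giving surveys at program visits.

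Entry depends on the arm. Protocol 8.4 times the pre-program research labs "immediately prior to the subject beginning the FFF program (month 0 for treatment group or approximately month 6 for the control group"). The 8.4.1 footnotes say "FFF program start will occur within 1 month after consent for" treatment patients, and "FFF program start will occur approximately 6 months after consent for" control patients.

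**The concern.** A subgroup of a randomized effect needs a defining variable whose value does not depend on assignment. Here assignment sets the date of measurement. A treated subject is scored at the start of follow-up, about six months before the primary outcome. A control is scored at about the time of that outcome, after a wait during which SAP 3.3 says controls can use usual-care dietitian consultations and diabetes classes. High and low knowledge then mean different things in the two arms.

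A second route is selection. The score is taken at FFF entry, and SAP section 4 accepts that some treated subjects may never join. Such people may have no score in either arm, and those who do present at month 0 need not resemble those who present at month 6.

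What is at stake is the reading of this one split. A difference in effect by knowledge would be taken as evidence about the role of information, when it could arise from the timing alone.

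**Working it through.** **1. Timing by arm**

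| | Treatment | Control |
|---|---|---|
| Program entry after consent (Protocol 8.4.1 footnotes) | within 1 month | about 6 months |
| Baseline survey (Protocol 8.4; SAP 3.1) | at entry, about month 0 | at entry, about month 6 |
| Primary HbA1c (SAP 3.2) | month 6 | month 6 |
| Gap from score to outcome | about 5 to 6 months | about none |

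No readable text describes a month-0 knowledge measure for controls. Recruitment is by telephone, with no survey mentioned (Protocol 8.2.4; SAP section 2). Protocol 12.1 explains why an earlier clinic visit is avoided. The survey row for controls in the 8.4.1 table did not survive text extraction, so the control timing comes from the prose and footnotes. Nothing readable contradicts it.

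**2. Illustration of size**

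The plan gives no figure for this split, so there is none to reproduce. The correlations below are assumptions; the documents give none.

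- Residual SD from SAP Table 2, HbA1c at 180 days: s = 1.74 × 0.66 = 1.148.
- r: correlation of month-0 with month-6 knowledge (0.5, 0.7, 0.9).
- b: correlation of residual HbA1c with month-0 knowledge.
- c: its correlation with the part of month-6 knowledge not predicted from month 0. Both b and c take the values 0, −0.1, −0.2, −0.3.
- The true effect is the same in everyone, and the median is pooled.

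For a standard normal score, the means above and below the median differ by 2√(2/π) = 1.596. The high-minus-low gap in HbA1c is 1.596·s·b in treatment (split on month-0 knowledge) and 1.596·s·[br + c√(1−r²)] in control (split on month-6 knowledge). The spurious interaction is the difference:

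1.833 × [b(1−r) − c√(1−r²)], since 1.148 × 1.596 = 1.833.

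- b = c = −0.2, r = 0.7: 1.833 × [−0.060 + 0.143] = +0.15.
- b = −0.3, c = −0.1, r = 0.5: 1.833 × [−0.150 + 0.087] = −0.12.
- All b = c cases other than zero: 0.06 to 0.23.

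Over the 48 combinations the range is −0.27 to +0.48 and the median absolute value 0.13. The result is positive in 33, negative in 12 and zero in 3. These counts describe the grid and are not probabilities. Simulation with 2,000,000 subjects per arm gave +0.152 and −0.121 for the two examples.

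A separate simulation used a slope of −0.2 HbA1c points per SD of knowledge. It gave about 0.10 (r = 0.7) and 0.16 (r = 0.5) in absolute value: positive if HbA1c follows current knowledge, negative if it follows earlier knowledge. With r = 1 and no drift it gave none. With r = 1 and control-only upward drift of 0.25 to 0.5 SD there was still no interaction, but both subgroup effects moved from −0.32 to between about −0.35 and −0.38.

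**3. Yardstick**

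The interaction SE for two equal halves is twice the overall SE. Two routes at N = 500, taking alpha 0.05 as two-sided (multiplier 2.80):

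- Table 2: 2 × (2 × 1.148/√500) = 0.205; detectable interaction 2.80 × 0.205 = 0.58.
- The SAP's detectable intent-to-treat effect, read as 3.7% of the Table 2 mean: 0.037 × 8.58 = 0.317; 0.317/2.80 = 0.113; 2 × 0.113 = 0.227; detectable interaction 2 × 0.317 = 0.63.

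If only 400 subjects had a score (assumed), the SEs would be 0.230 and 0.253. The median bias of 0.13 is about 0.6 of an SE (0.13/0.205 = 0.63; 0.13/0.227 = 0.57).

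**The case against.** The best defence is that the score precedes FFF exposure in both arms. That stands. A reader might infer that the program itself contaminates the controls' scores, but the documents do not support this: controls are surveyed on entry, and Protocol 12.1 avoids earlier clinic visits for this very reason. What the defence leaves open is elapsed time, usual care and selective attendance.

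It can also be said that the item is tentative, one of about ten heterogeneity analyses, with no confirmatory claim attached. That stands too and sets the severity.

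The arithmetic is open to challenge. Nothing in the documents supports correlations as large as 0.3 with what remains of HbA1c after adjustment for baseline, so the grid's extremes are not plausible bounds. The grid also has no term for selective attendance or a mean shift in control knowledge. In 34 of its 48 combinations the bias is below 0.205. It shows that the artefact can exist and that its sign is not predictable, and no more.

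Protocol 8.4 also offers telephone or e-mail surveys to people who leave the program but stay in the study. If that is read to cover people who never start, some missing scores would be filled. The timing difference would remain.

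**Conclusion.** The point holds as a minor one. Confidence is high on the timing, which both documents state, and low on size and direction, which rest on assumed correlations. If knowledge is stable, without drift or selective entry, the bias is zero. Otherwise a plausible order of size is 0.1 to 0.2 HbA1c points, under one interaction SE and well under the detectable interaction of about 0.58 to 0.63.

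Three stronger readings go too far. A reader might infer that the split would hide or reverse a real difference by knowledge. The calculations cover only a uniform true effect, where there is no difference to hide, so they show only that a spurious one can appear. A reader might infer that the main result is at risk. It is not: the primary intent-to-treat comparison does not use the survey, and subgroups defined from pre-enrollment data (HbA1c stratum, site, sex, payer, insulin at the start) are unaffected. A reader might also infer from SAP section 2 that recruiters have no contact with controls before month 5. It says that they call then to book appointments, not that this is the only contact.

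The issue may also reach a little further than this split. SAP section 4 plans to test changes in survey indexes, and the lack of a described month-0 control survey may affect those tests as well.

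**What to change.** In SAP section 4, Planned Heterogeneity Analysis, add after the median-split sentence: *The knowledge score is taken at FFF entry, about month 0 in the treatment group and about month 6 in the control group, so the comparison by knowledge is non-randomized and descriptive.* Alternatively, take the split out of the heterogeneity analyses of the randomized effect.

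Either change needs no new data, and SAP section 1 already provides for dated revisions. The cost is that this one exploratory split no longer supports a causal statement about initial knowledge.

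This labels the problem and does not repair it. A repair would need a knowledge measure in both arms before assignment is revealed, for example at the recruitment call. That adds data collection and helps only subjects not yet randomized. It is an option and is not needed to settle the point.
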